July 19, 2024

Protocol:

**Retrospective study on anti-cancer systematic therapy for
gastric cancer patients complicated with bleeding**

Retrospective study on anti-cancer systematic therapy for gastric cancer patients complicated with bleeding

Abstract

BACKGROUND

Hemorrhage isn't a rare complication with gastric cancer (GC)/gastroesophageal junction cancer (GEJC) and may lead to poor prognosis.

AIM

To investigate the impact of overt bleeding (OB) on the survival and treatment related adverse events (TRAEs) of GC/GEJC patients.

METHODS

This study will retrospectively enroll advanced or metastatic GC/GEJC patients who received systematic treatment at Peking University Third Hospital. The study aims to investigate the impact of OB on TRAEs for GC/GEJC patients receiving anti-cancer treatment, evaluate the risk factors of overt bleeding after treatment (OBAT), assess the influence of overt bleeding on the overall survival (OS).

Key words: Gastric cancer (GC)/gastroesophageal junction cancer (GEJC), Overt bleeding (OB), Systematic treatment

INTRODUCTION

Gastric cancer was the fifth most common cancer and ranked fourth for cancer mortality worldwide in 2020[1]. Hemorrhage wasn't a rare complication with gastric cancer (GC)/gastroesophageal junction cancer (GEJC). About 15.7% of GC/GEJC patients experienced bleeding[2]. Hemorrhage not only reduced the quality of life in GC/GEJC patients, but also led to poor prognosis even life-threatening if it was failure to timely stop and affected anti-cancer treatment[3, 4].

Risk factors for hemorrhage with GC/GEJC were various, including oldness, smoking history, chronic disease, use of antithrombotic/anticoagulants and so on[2, 5]. Radical gastrectomy was an ideal for early stage GC/GEJC with overt bleeding (OB),

but there was no curable chance for patients with advanced or metastatic GC/GEJC and hemostatic strategies such as endoscopic therapy, transcatheter arterial embolization were prone to rebleeding[4, 6, 7]. GC/GEJC patients with hemorrhage were less likely to receive chemotherapy due to poor physical quality and concern about treatment related adverse events (TRAEs) and rebleeding.

The retrospective study aims to investigate the impact of OB on TRAEs for GC/GEJC patients receiving anti-cancer treatment, assess the influence of overt bleeding on the overall survival (mOS).

PATIENTS AND METHODS

Data source and study patients

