We will retrospectively enroll patients who were diagnosed with advanced or metastatic GC/GEJC at department of medical oncology and radiation sickness of Peking University third hospital. The eligibility criteria are as follows: 1) patients older than 18 years. 2) a histologically confirmed diagnosis of advanced or metastatic GC/GEJC. 3) the initial anti-cancer treatment was systematic therapy, including chemotherapy, targeted therapy or immune checkpoint inhibitor (ICI). 4) no history of gastrectomy before systematic therapy. The exclusion criteria included: 1) incompletable clinical data. 2) Siewert I type esophagus cancer.

The patients information collected from the database is as follows: age, gender, height, weight, Eastern Corporative Oncology Group Performance Status (ECOG-PS), chronic disease, drinking history, smoking history, diagnosis and metastatic sites, primary tumor location, histological grade, clinical stage according to the 8th edition of AJCC (American Joint Committee on Cancer) cancer staging manual, overt bleeding, symptoms, therapy strategy, tumor response to treatment, objective response rate (ORR), disease control rate (DCR), TRAEs and media overall survival (mOS).

Definitions

The diagnosis of OB is that the following conditions occurred one month before systematic treatment: 1) melena, hematemesis or hematochezia caused by gastric lesion, or 2) gastric hemorrhage confirmed by endoscopy. This study will only

analyze the impact of gastric overt bleeding (not including occult bleeding) on patients.

The radiographic best response to treatment will be assessed as complete response (CR), partial response (PR), stable disease (SD), no CR or no progressive disease (PD), or PD on the basis of response evaluation criteria in solid tumor 1.1 by clinicians. Objective response rate (ORR) is defined as the proportion of patients with the best response CR or PR. Disease control rate (DCR) is defined as the proportion of patients whose best response was CR, PR, no CR or no PD, or SD. Patients will be followed up at regular intervals. The criterion for terminating follow-up is death for any reason. OS is defined as the time from the first cycle of systematic therapy to death from any cause. TRAEs are evaluated according to the National Cancer Institute Common Toxicity Criteria version 4.0.

Statistical analysis

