We will use SPSS version 25.0 (International Business Machines, New York, United States) to analyze the data and considered that differences are statistically significant if the two-sided P values are less than 0.05. The classified variables will be assessed by the χ^2 test or Fisher's exact test. A binary logistic regression model (entry method) will be used to identify items independently associated with OBAT. Odds ratios (ORs) and 95% confidence intervals (CIs) will be calculated. Survival curves will be estimated by the Kaplan-Meier method with the log-rank test. Hazard ratios (HRs) and 95%CIs will be calculated using the Cox proportional hazards model, and a check on the assumption of proportional risk will be conducted.

CONCLUSION

In conclusion, this study aims to evaluate the efficacy and safety of systematic therapy on GC/GEJC patients with bleeding. We hope the study will provide basis for future prospective clinical trial.

Institutional review board statement: This study was approved by the Peking University Third Hospital Medical Science Research Ethics Committee (IRB00006761-M2023544).

Informed consent statement: A waiver of informed consent was granted by the Ethics Committee.

REFERENCES

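### The comparison of TRAEs by overt bleeding may partly measure the bleeding itself: TRAE terms, attribution and baseline rules are unset, and no baseline haemoglobin is collected

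*Combined protocol and SAP*

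**What the plan says.** The Abstract puts this question first among the objectives: "The study aims to investigate the impact of OB on TRAEs for GC/GEJC patients receiving anti-cancer treatment". The Introduction repeats it.

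Definitions sets the exposure: "The diagnosis of OB is that the following conditions occurred one month before systematic treatment", followed by visible gastrointestinal bleeding from the gastric lesion, or "gastric hemorrhage confirmed by endoscopy".

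The outcome gets one sentence in the same section: "TRAEs are evaluated according to the National Cancer Institute Common Toxicity Criteria version 4.0". There is no list of event terms, no rule for deciding that an event is treatment related, and no rule for conditions already present before the first cycle.

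The data list in Data source and study patients runs from demographics and performance status through "overt bleeding, symptoms, therapy strategy, tumor response to treatment" to response, TRAEs and survival. It has no haemoglobin, transfusion or other laboratory item.

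OBAT is a separate outcome, with its own objective in the Abstract and its own logistic model in Statistical analysis. The protocol does not define it further or say whether an OBAT event is also a TRAE.

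For TRAE rates, the only applicable method in Statistical analysis is the general one: "The classified variables will be assessed by the χ^2 test or Fisher's exact test".

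**The concern.** The exposure is blood loss from the stomach. Low haemoglobin and further bleeding are foreseeable consequences of it; the Introduction itself notes that bleeding tends to recur after haemostatic measures. If either is recorded as a TRAE, OB patients can show a higher TRAE rate although the drugs are no more toxic to them. If chart reviewers who know the bleeding history put anaemia down to the tumour in OB patients and to the drug in the others, the OB rate is pushed down instead. Without a pre-treatment haemoglobin, neither effect can be separated out afterwards.

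The result matters for use. The Introduction says patients with bleeding are less likely to receive chemotherapy, partly from concern about TRAEs, and the Conclusion hopes the study will inform a prospective trial. An artefact could reinforce that concern or hide a real difference.

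**Working it through.** **No figure to reproduce.** The protocol gives no sample size, TRAE rate or effect size. Everything below is illustration. The only document figure used is the 15.7% bleeding proportion in the Introduction, borrowed to set a group split; it describes bleeding in gastric cancer generally, not OB as defined here.

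**Step 1: what keeps exposure and outcome apart.**
- Time: OB is limited to the month before treatment. This separates the bleeding episode from later events, but not its consequences.
- Attribution: the outcome is named treatment related, but no method is given.
- Baseline: no rule, and no haemoglobin with which to apply one.
- OBAT: a separate outcome, with overlap with TRAEs left open.
- Analysis: unadjusted. The logistic model is named for OBAT only.

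**Step 2: upward bias.** Let the drug-caused TRAE risk be p in both groups, and let a share q of OB patients have a bleeding-caused event recorded as a TRAE, independently. Then the OB rate = 1 − (1 − p)(1 − q), against p without OB. Example: p = 0.20, q = 0.10 gives 1 − 0.80 × 0.90 = 0.28, and the odds ratio is (0.28/0.72)/(0.20/0.80) = 1.56.

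The last column is the chance of a two-sided P < 0.05 in the direction of more TRAEs with OB. It uses the normal approximation for two proportions with an assumed N = 200, of whom 0.157 × 200 ≈ 31 have OB.

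| p | q | OB rate vs non-OB | Odds ratio | Chance of P < 0.05 |
|---|---|---|---|---|
| 0.20 | 0.10 / 0.20 / 0.30 | 28 / 36 / 44% vs 20% | 1.56 / 2.25 / 3.14 | 19 / 50 / 79% |
| 0.40 | 0.10 / 0.20 / 0.30 | 46 / 52 / 58% vs 40% | 1.28 / 1.62 / 2.07 | 9 / 24 / 46% |
| 0.60 | 0.10 / 0.20 / 0.30 | 64 / 68 / 72% vs 60% | 1.19 / 1.42 / 1.71 | 6 / 12 / 23% |

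Over N = 100 to 400 the last column runs from about 5% to 97%. With q = 0 the two rates are equal and the test has its nominal 5% error.

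**Step 3: downward bias.** Suppose instead that a share s of drug-caused TRAEs in OB patients is credited to the tumour and not recorded. The OB rate is then p(1 − s). At p = 0.40 and s = 0.30 it is 0.40 × 0.70 = 28% against 40%, odds ratio (0.28/0.72)/(0.40/0.60) = 0.58. With both mechanisms the OB rate = 1 − (1 − p(1 − s))(1 − q). At p = 0.40:
- s = 0.30, q = 0.10: 1 − 0.72 × 0.90 = 35.2%, below 40%.
- s = 0.10, q = 0.30: 1 − 0.64 × 0.70 = 55.2%, above 40%.

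The sign depends on shares that the documents do not give.

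**Step 4: anaemia, if it were recorded on a fixed haemoglobin threshold.** That recording rule is itself an assumption. Assume a threshold of 8 g/dL, baseline SD 1.5, and the same drug-related fall of 1.5 (SD 1.2) in both groups. P(nadir < 8) = Φ((8 − (baseline mean − 1.5))/√(1.5² + 1.2²)). A baseline mean of 12 gives 9.7%; means of 11, 10 and 9.5 give 21.7%, 39.7% and 50.0%. This model treats every low value as a TRAE and ignores attribution, transfusion and recovery after bleeding, so it shows the upward direction only.

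**The case against.** A reader might infer that the endpoint counts anaemia and gastric haemorrhage. The documents do not support that. They list no TRAE terms and never mention anaemia, and the content of the cited grading criteria is not reproduced. What the text shows is that these events are not excluded.

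The sponsor could add that a treatment-related event must by name be attributed to treatment, so a condition present before the first dose should not qualify; that OBAT is already kept as its own outcome; and that TRAEs may be reported term by term rather than as one total. Each point has weight and rules out saying that nothing separates exposure from outcome. None closes the gap: attribution made from charts that record the bleeding history, under no stated rule, is itself a source of bias, and OBAT's relation to TRAEs is not stated.

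The strongest objection concerns the remedy. If OB patients become more anaemic on the same drug, that may be a genuine effect of OB on tolerability, and removing all anaemia from the main comparison would discard truly drug-related anaemia. That stands, and is why the fix counts worsening from baseline and shows both versions.

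It is also tempting to read the illustrations as an estimate of the bias, or as showing that it favours non-OB patients. All their inputs are assumed, and Step 3 shows that the direction can reverse.

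**Conclusion.** The concern holds in a limited form. Followed as written, the plan allows blood loss or rebleeding arising from the exposure to enter the outcome, and it collects nothing that would let an analyst separate the two later. This affects a lead objective, so it is more than a missing detail.

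The size and net direction are unknown. With equal drug toxicity, the one-directional model gives odds ratios from 1.19 to 3.14 over the assumed range, and differential attribution can take the ratio below 1. These figures show that an apparent difference can arise with none in toxicity; they do not predict what this study will find. That the data list lacks haemoglobin and that the TRAE rules are absent rests on the text alone and needs no assumption.

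**What to change.** In Data source and study patients, add two items: the last haemoglobin before cycle 1, and any pre-treatment transfusion.

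In Definitions, add a short paragraph stating that:
- anaemia counts as a TRAE only if it worsens by at least one grade over the baseline grade, applied identically in both groups;
- gastric bleeding after treatment start is counted under OBAT only, with a sentence saying what qualifies as OBAT, including how bleeding that continues from before treatment is handled.

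In Statistical analysis, report the OB-versus-no-OB TRAE comparison both with and without anaemia and bleeding terms, and conclude that OB affects drug tolerability only if the result does not depend on those terms.

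Cost: two extra chart fields, one paragraph, and a somewhat lower TRAE count. The study is retrospective, so no patient's care changes. The baseline-change measure is imperfect: transfusion or recovery after a bleed can still affect it, which is why transfusion is recorded and both versions are shown.

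### Risk factors for bleeding after treatment (OBAT) go into a yes/no logistic model with no time window and no rule for death or unequal follow-up, so odds ratios for prognostic factors can mix bleeding with survival

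*Combined protocol and SAP*

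**What the plan says.** The METHODS paragraph of the Abstract lists, as one of three aims, to "evaluate the risk factors of overt bleeding after treatment (OBAT". The Statistical analysis section assigns this outcome by name to one method: "A binary logistic regression model (entry method) will be used to identify items independently associated with OBAT". The effect measure follows: "Odds ratios (ORs) and 95% confidence intervals (CIs) will be calculated".

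The Definitions section defines only bleeding before treatment: "The diagnosis of OB is that the following conditions occurred one month before systematic treatment". It gives OBAT no start, end or horizon. On follow-up it says "The criterion for terminating follow-up is death for any reason", with no common cut-off date and no minimum duration.

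The data list under Data source and study patients includes "overt bleeding, symptoms, therapy strategy, tumor response to treatment" but names no date for a bleed after treatment.

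Time-to-event methods do appear: "Survival curves will be estimated by the Kaplan-Meier method with the log-rank test", and then "Hazard ratios (HRs) and 95%CIs will be calculated using the Cox proportional hazards model". The Cox sentence names no outcome, but it follows the sentence on survival curves, and OBAT has already been given to logistic regression. No competing-event method, person-time adjustment, landmark or censoring rule is given for OBAT.

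**The concern.** These patients have advanced or metastatic disease, and death without a bleed ends the chance of having one. If OBAT is recorded as ever or never over whatever follow-up exists, a patient who dies at 2 months without bleeding counts the same as one who lives 3 years without bleeding. Time at risk then differs between patients and depends on survival.

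The odds ratio still describes who bled before death or last contact. It does not describe how a factor changes the risk of bleeding while the patient is alive, which is how a risk-factor analysis is usually read. A factor that shortens survival has its bleeding effect understated, and one that lengthens survival has it overstated. Performance status, stage and metastatic sites are all collected and are plausible examples. The model's covariates are not listed.

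A real bleeding risk factor in frail or high-burden patients could therefore be missed, in a study whose Conclusion hopes to inform a prospective trial.

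**Working it through.** The plan states no sample size, event count, OBAT rate or power, so there is no figure of its own to reproduce. The check is of the mechanism.

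**Inputs from the documents.** Binary logistic model with odds ratios; two-sided 0.05 level; follow-up ending at death; no OBAT window.

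**Assumptions, not in the documents.**
- Constant hazards.
- Reference median 12 months to death without bleeding.
- Reference OBAT risk of 15.7% if followed to death. This borrows the Introduction's general bleeding proportion, which is not an OBAT rate.
- Factor prevalence 30%.
- Censoring uniform over 12 to 60 months.

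Below, death HR means the hazard ratio for death without prior bleeding, not the overall-survival hazard ratio.

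**Formula.** With bleeding hazard b and hazard d of death without bleeding,

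P(OBAT by w) = b/(b+d) × [1 − exp(−(b+d)w)].

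With follow-up to death the odds are b/d, so OR = bleeding HR / death HR exactly. A factor with no effect on bleeding then has OR 1/1.5 = 0.67 or 1/2 = 0.50 at death HR 1.5 or 2. A factor that doubles both hazards has OR 2/2 = 1.00. One with bleeding HR 2 and death HR 3 has OR 2/3 = 0.67, which reverses its direction.

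**With censoring.** Reference d = ln 2/12 = 0.0578 per month and b = 0.0578 × 0.157/0.843 = 0.0108. Averaging P over the censoring times gives a reference risk of 0.1368. For bleeding HR 2 and death HR 1.5 the risk is 0.1885, so OR = (0.1885/0.8115)/(0.1368/0.8632) = 1.47.

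The table adds rejection rates from a simulation with N=300, Wald tests and 12,000 replicates (Monte Carlo standard error at most 0.5 points). Each pair is logistic / cause-specific Cox.

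| Death HR | OR, bleeding HR 1 | OR, bleeding HR 2 | Rejection, bleeding HR 1 | Power, bleeding HR 2 |
|---|---|---|---|---|
| 1 | 1.00 | 2.04 | 4.5% / 4.4% | 60% / 67% |
| 1.25 | 0.84 | 1.71 | 5.6% / 4.4% | 37% / 62% |
| 1.5 | 0.73 | 1.47 | 9.7% / 4.3% | 21% / 59% |
| 2 | 0.56 | 1.13 | 22.9% / 3.9% | 6% / 52% |

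**Sensitivity.**
- Reference OBAT risk of 10%, 15.7% or 25%: the OR for bleeding HR 2 and death HR 1.5 is 1.47, 1.47 or 1.46.
- Censoring uniform over 6 to 36 months: that OR is 1.59, and for bleeding HR 1 it is 0.78.
- Other sample sizes at death HR 1.5 (4,000 replicates): rejection with bleeding HR 1 is 4.0% / 3.1% at N=150 and 17.8% / 4.2% at N=600. Power with bleeding HR 2 is 12% / 34% and 37% / 86%.

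**Dependence on the window.** For bleeding HR 2 and death HR 1.5:

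| Window | OR |
|---|---|
| 3 months | 1.94 |
| 6 months | 1.88 |
| 12 months | 1.75 |
| 24 months | 1.56 |
| To death | 1.33 |

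**Unequal follow-up alone.** Suppose a factor affects neither bleeding nor death, but one group is observed for 12 months and the other for 24. The OBAT risks are 8.8% and 12.7%, so OR = (0.088/0.912)/(0.127/0.873) = 0.66 from these rounded risks (0.67 unrounded).

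**The case against.** The strongest reply is that the harm depends on a window the documents do not state. They show that it is undefined, not that OBAT will be counted to death. With a 3- or 6-month window the distortion is small. That is correct, and the conclusion is conditional on it. But the same data could then give materially different odds ratios depending on a choice the plan does not make.

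Second, the odds ratio for bleeding before death is a legitimate risk measure over a fixed, fully observed window. If a factor leaves the bleeding hazard alone but shortens survival, its carriers really do bleed less often, so rejecting an odds ratio of 1 is right for that target. This stands: the 22.9% is an error rate only if the effect on bleeding while alive is the target. The plan does not say which it wants.

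Third, the simulation uses one unadjusted binary factor and proportional hazards, while the plan adjusts for several items. What matters is each factor's death HR given the other covariates, which may be smaller than the crude one. Adjustment does not remove the problem for factors that are themselves prognostic.

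Fourth, OBAT is absent from the AIM statement, the closing aim of the Introduction and the Conclusion. That limits the importance of the point but does not remove it.

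**Conclusion.** The concern holds. OBAT risk factors are a listed aim, the stated method is a yes/no model, and nothing in the documents gives OBAT a window or deals with death or unequal follow-up. If OBAT is counted over open-ended follow-up, the odds ratio for any factor that also affects survival mixes the two effects.

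In the illustration, a bleeding HR of 2 gives an odds ratio of 1.47 at death HR 1.5 and 1.13 at death HR 2, and logistic power at N=300 falls to 21% and 6%, against 59% and 52% for cause-specific Cox. These figures rest wholly on assumed hazards, censoring and sample size, and on the bleeding hazard while alive being the target. Certainty is high about the omission and the direction of the distortion, and low about its size in this study. Factors unrelated to survival are little affected by death, although unequal follow-up can still distort them. The point does not bear on the overall-survival analysis. It should be fixed, but it touches one aim only.

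**What to change.** - Define OBAT as a new overt gastric bleed after the first cycle, and record its date.
- Replace the logistic model with cause-specific Cox regression of time from first cycle to first OBAT. Censor at last contact, treat death without OBAT as a competing event, and use only covariates known at the first cycle.
- Report the Aalen-Johansen cumulative incidence of OBAT by baseline bleeding status, so that absolute risk is shown beside the hazard ratios.
- If dates cannot be retrieved for everyone, use one short common window (for example 3 or 6 months) for all patients. State how deaths and incomplete follow-up inside it are handled, and say that the odds ratio refers to that window. This reduces the distortion but does not remove it.

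**Cost.** One definition, one date field and one rewritten sentence. Cox regression is already planned. The data list does not name an OBAT date, so retrievability must be checked. That list does not name first-cycle or death dates either, though overall survival needs them, so its silence settles little. There is extra record extraction, a slightly longer report, and a check that the planned software can produce cumulative incidence.

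The fallback window costs events. At N=300 with bleeding HR 2 and death HR 1.5, 300 × (0.3 × 0.0950 + 0.7 × 0.0529) gives about 20 OBAT events in 6 months. Over all follow-up, 300 × (0.3 × 0.1885 + 0.7 × 0.1368) gives about 46. At 6 months power is 27% for logistic and 33% for Cox, against 59% for Cox over all follow-up.

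### The effect of overt bleeding on TRAEs is a stated aim, but the plan names no analysis for it; by inference the comparison is an unadjusted chi-square or Fisher test, which may be confounded in an unknown direction.

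*Combined protocol and SAP*

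**What the plan says.** The effect of OB on TRAEs appears as an aim three times: in the Aim and the Methods of the Abstract, and at the end of the Introduction. The Abstract's Methods put it this way: "The study aims to investigate the impact of OB on TRAEs for GC/GEJC patients receiving anti-cancer treatment". The Conclusion gives the same purpose in broader terms: "this study aims to evaluate the efficacy and safety of systematic therapy on GC/GEJC patients with bleeding".

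Under Definitions, OB is a baseline exposure ("The diagnosis of OB is that the following conditions occurred one month before systematic treatment") and TRAEs have a grading system ("TRAEs are evaluated according to the National Cancer Institute Common Toxicity Criteria version 4.0"). No TRAE endpoint, such as any grade, severe grade or a composite, is singled out.

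The Statistical analysis section contains these methods:

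- for categorical variables, "The classified variables will be assessed by the χ^2 test", with Fisher's exact test as the alternative;
- for OBAT, "A binary logistic regression model (entry method) will be used to identify items independently associated with OBAT", followed by "Odds ratios (ORs) and 95% confidence intervals (CIs) will be calculated", a sentence that names no outcome of its own;
- Kaplan-Meier curves with the log-rank test, and a Cox model for hazard ratios.

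No sentence in that section names TRAEs.

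**The concern.** OB is observed, not assigned. The Introduction itself says that bleeding goes with older age, smoking, chronic disease and antithrombotic use, and that bleeding patients are in poorer physical condition and receive chemotherapy less often. Any of these could also change the risk of toxicity. A crude contrast of TRAE rates would then mix the effect of OB with differences in patient profile or in treatment received.

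The study hopes to provide a basis for a prospective trial, so its safety comparison will be read as evidence on whether patients with bleeding tolerate systemic therapy. The reader could not correct a crude result mentally, because the likely distortions point in opposite directions. If only a P value were given, a non-significant result could be taken as reassurance even where the data are imprecise. The plan looks for independent associations with OBAT but describes nothing comparable for TRAEs.

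**Working it through.** **Step 1: match aims to methods.** The documents give no sample size, TRAE rate or event count, so there is no figure of the plan's own to reproduce.

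| Aim | Method in Statistical analysis | Adjusted? |
|---|---|---|
| Risk factors for OBAT | Binary logistic regression, ORs with 95% CIs | Yes, covariates not listed |
| OB and overall survival | Kaplan-Meier, log-rank, Cox | Possible through Cox, covariates not listed |
| OB and TRAEs | None named; by inference chi-square or Fisher | No adjustment mentioned |

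The sentence on odds ratios directly follows the OBAT model and most naturally belongs to it.

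**Step 2: confounding by fitness.** All inputs are assumptions: no true OB effect, TRAE risk 50% with poor ECOG-PS and 30% otherwise, poor ECOG-PS in 15% of non-OB patients. Marginal risk = q × 0.50 + (1 − q) × 0.30, where q is the share with poor ECOG-PS.

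- Non-OB: 0.15 × 0.50 + 0.85 × 0.30 = 0.330.
- OB, q = 40%: 0.380; crude OR = (0.380/0.620)/(0.330/0.670) = 1.24.
- OB, q = 25%: 0.350; crude OR = (0.350/0.650)/(0.330/0.670) = 1.09.
- OB, q = 15%: 0.330; crude OR = 1.00.
- OB, q = 10% (OB group fitter): 0.320; crude OR = 0.96.

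**Step 3: false-positive rate of the chi-square test.** This is an exact binomial calculation at a nominal two-sided 5%, without continuity correction. The OB counts apply the Introduction's 15.7% background bleeding figure (0.157 × 200 = 31.4, taken as 31; 0.157 × 400 = 62.8, taken as 63). That figure is not this cohort's OB share.

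| Poor ECOG-PS in OB | N = 200 (31 OB) | N = 400 (63 OB) |
|---|---|---|
| 40% | 9.3% | 12.6% |
| 25% | 5.9% | 6.4% |
| 15% | 5.0% | 5.0% |

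In simulation under the same inputs (4,000 runs per setting), a logistic model with OB and ECOG-PS rejected in 4.8% to 5.4% of runs at N = 200 and N = 400. At N = 100, where data are sparse, it rejected in 2.8% to 3.9%.

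**Step 4: direction.** A second set of assumptions uses a base risk of 20% or 40%, no OB effect, and a factor that raises TRAE odds 2- to 3-fold.

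- Poor fitness in 40–50% of OB against 20% of non-OB patients: crude OR 1.15 to 1.41.
- More toxic treatment in 40–50% of OB against 70% of non-OB patients: crude OR 0.72 to 0.88. For example, at base risk 20% and a 3-fold factor, exposed risk = 0.75/1.75 = 0.429. The OB risk is 0.6 × 0.20 + 0.4 × 0.429 = 0.291, the non-OB risk is 0.3 × 0.20 + 0.7 × 0.429 = 0.360, and the OR is 0.73.
- Both at 2-fold (40% against 20%; 50% against 70%): crude OR 1.00 to 1.01.

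The distortion can go up, go down or cancel.

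**Step 5: precision.** Assuming 35% risk in both groups, the crude 95% CI for the OR is the estimate multiplied or divided by exp(1.96 × √[1/(n₁ × 0.35 × 0.65) + 1/(n₀ × 0.35 × 0.65)]). This is 2.23 at N = 200 (31 OB, 169 non-OB) and 1.76 at N = 400 (63 and 337). The simulated ECOG-PS-adjusted factors are 2.33 to 2.36 and 1.80 to 1.81. An observed OR of 1.0 would thus have an upper crude limit of about 2.2 at N = 200 and 1.8 at N = 400.

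**The case against.** Four objections deserve weight.

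- **The plan is silent; it does not choose a crude test.** A reader might infer that an unadjusted TRAE comparison has been selected. The documents do not say so, and an adjusted analysis that was intended but not written down cannot be ruled out. This stands. The defect is a missing specification, and the chi-square reading is an inference.
- **A fitness gap need not go unseen.** A reader might infer that nothing in the plan would reveal imbalance. The generic sentence on categorical variables, if it reaches TRAEs, reaches ECOG-PS by OB as well. Such a table could show a gap, though it would not adjust for it.
- **The gap may be small.** Eligibility requires that "the initial anti-cancer treatment was systematic therapy, including chemotherapy, targeted therapy or immune checkpoint inhibitor (ICI", so the least fit bleeding patients may never enter. This stands too. It is why the illustration runs down to no gap at all, where the crude test behaves as it should.
- **Adjusting for ECOG-PS may remove part of what is sought.** Poor condition may be a consequence of bleeding. If the total effect of OB is wanted, ECOG-PS lies partly on the causal path, and the same holds for the therapy chosen after OB. This also stands, and it shapes the fix. It does not excuse leaving out age, smoking and chronic disease, which the Introduction lists as risk factors for bleeding.

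**Conclusion.** The point holds as a gap in specification. A stated aim has no named analysis, and the only method that can be read as covering it makes no adjustment for factors that the protocol itself associates with bleeding.

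It would go too far to say that the result will be biased, or that toxicity in OB patients will be overstated. The documents give no TRAE rates, ECOG-PS mix or treatment mix by group, and plausible inputs move the crude odds ratio either way. The illustrative false-positive rates, from 5.0% to 12.6%, rest wholly on assumptions; with a gap reduced by eligibility (25% against 15%) the inflation is about one percentage point. Adjustment deals with measured confounding only. It does not cure imprecision, which a confidence interval makes visible.

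This should be changed before the data are analysed. It does not invalidate the study. Confidence is medium, because an unwritten adjusted analysis remains possible.

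**What to change.** In Statistical analysis, add a binary logistic model for one TRAE composite defined in advance:

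- OB is the exposure. Covariates are baseline factors already collected and fixed beforehand: age, chronic disease and smoking, plus stage if the number of events allows.
- Report the adjusted OR with 95% CI next to the crude OR with 95% CI. Keep chi-square and Fisher tests for descriptive tables.
- State whether the total or the direct effect of OB is wanted. Show results with and without ECOG-PS, since it may partly result from OB. Only the version with ECOG-PS removes the distortion illustrated in steps 2 and 3 of the working.
- Treat adjustment for therapy strategy as a sensitivity analysis, for the same reason.

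**Cost.** The model needs no new variables: all those named are on the data list, and logistic regression in SPSS is already planned. The adjusted interval is slightly wider (a factor of about 2.3 to 2.4 against 2.2 at an assumed N of 200).

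The number of covariates is limited by the number of TRAE events. With four coefficients (OB, age, chronic disease, smoking, one each), N = 200 gives 200 × 0.35/4 = 17.5 events per coefficient at 35% risk, but 200 × 0.15/4 = 7.5 at 15%. At N = 100 the figures are 8.75 and 3.75.

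Antithrombotic use, which the Introduction names as a bleeding risk factor, is not on the data list. It may not be available for adjustment and should be acknowledged as a possible source of residual confounding.
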